10.5 Reporting Requirements

10.5.1 Expedited Reporting Requirements

All SAEs and EOSI that occur during the course of the AE Reporting Period (refer to Section 10.3.1), whether or not considered related to study drug, must be reported by entering the information in the AE eCRF and submitting to BPV within 24 hours of the site becoming aware of the event. Investigators should not wait to collect information that fully documents the event before notifying BPV of an SAE. BioMarin may be required to report certain SAEs to regulatory authorities within 7 calendar days of being notified about the event; therefore, it is important that Investigators submit any information requested by BioMarin as soon as it becomes available.

The Sponsor is responsible for identifying, preparing and reporting all SUSARs to the relevant competent authorities, ethics committees and investigators in accordance with the requirements identified in the Clinical Trials Regulations.

If the EDC is unavailable, all SAEs should be reported to BPV by completing the SAE Report Form and faxing or emailing the completed form to BPV within 24 hours of the site becoming aware of the event. Once the EDC is available, the information should be entered in the AE eCRF.

10.5.2 Ethics Committee Reporting Requirements

Reporting of SAEs to the Independent Ethics Committee (IEC) will be done in compliance with the standard operating procedures and policies of the IEC and with applicable regulatory requirements. Adequate documentation must be obtained by BioMarin showing that the IEC was properly and promptly notified as required.

10.6 Follow-up of Subjects after Adverse Events

The Investigator should follow all unresolved AEs and SAEs until the events are resolved or have stabilized, the subject is lost to follow-up, or it has been determined that the study treatment or participation is not the cause of the AE/SAE. Resolution of AEs and SAEs (with dates) should be documented on the AE eCRF and submitted to BioMarin Pharmacovigilance and in the subject's medical record to facilitate source data verification.

For some SAEs, the Sponsor may follow up by telephone, fax, electronic mail, and/or a monitoring visit to obtain additional case details (eg, hospital discharge summary, consultant report, or autopsy report) deemed necessary to appropriately evaluate the SAE report.

10.7 Post-Study Adverse Events

At the last scheduled visit, the Investigator should instruct each subject to report, to the Investigator and/or to BPV directly, any subsequent SAEs that the subject's personal physician(s) believes might be related to prior study treatment.

The Investigator should notify the study Sponsor of any death or SAE occurring at any time after a subject has discontinued or terminated study participation, if the Investigator believes that the death or SAE may have been related to prior study treatment. The Sponsor should also be notified if the Investigator should become aware of the development of cancer or of a congenital anomaly in a subsequently conceived offspring of a subject that participated in this study.

10.8 Urgent Safety Measures

The regulations governing clinical trials state that the Sponsor and Investigator are required to take appropriate urgent safety measures to protect subjects against any immediate hazards that may affect the safety of subjects, and that the appropriate regulatory bodies should be notified according to their respective regulations. According to the European Union (EU) Clinical Trial Directive 2001/20/EC, "...in the light of the circumstances, notably the occurrence of any new event relating to the conduct of the trial or the development of the investigational medicinal product where that new event is likely to affect the safety of the patients, the Sponsor and the Investigator shall take appropriate urgent safety measures to protect the patients against any immediate hazard. The Sponsor shall forthwith inform the competent authorities of those new events and the measures taken and shall ensure that the IRB/IEC/REB is notified at the same time."

The reporting period for these events which may require the implementation of urgent safety measures is the period from the time of signing of the ICF through the completion of the last study visit or at the Early Termination Visit (ETV). Investigators are required to report any events which may require the implementation of urgent safety measures to BioMarin within 24 hours.

Examples of situations that may require urgent safety measures include discovery of the following:

- Immediate need to revise the IP administration (eg, modified dose amount or frequency not defined in protocol)
- Lack of study scientific value, or detrimental study conduct or management
- Discovery that the quality or safety of the IP does not meet established safety requirements

BOMARIN	270-201 – Amendment 3	Page 64

11 APPROPRIATENESS OF MEASUREMENTS

The measures of efficacy to be used in this study are standard, ie, widely used and generally recognized as reliable, accurate, and relevant (able to discriminate between effective and ineffective agents). The measures of safety used in this study are routine clinical and laboratory procedures.

The chromogenic FXa assay and the APTT assays are both validated and utilize CE marked reagents. The exploratory FVIII activity assay will be used for exploratory purposes only.

12 STUDY PROCEDURES

12.1 Prestudy

An ICF must be signed and dated by the patient, the Investigator or designee and witness (if required) before any study-related procedures are performed.

12.2 Screening Visit

Screening assessments will be performed within 28 days (\pm 14 days) of BMN 270 infusion while baseline assessments will take place within 7 days of BMN 270 infusion (Day 1). Should the screening visit occur within 7 days of the drug infusion, physical examination, vital signs, blood chemistry, haematology, urine tests, coagulation screen, and CRP do not need to be repeated at Baseline.

The following procedures will be performed during the Screening Period:

- Full medical history, including haemophilia A history, Hepatitis B, Hepatitis C, and HIV.
- Complete Physical Exam (including height and weight)
- Vital Signs (systolic and diastolic blood pressure, heart rate, respiration rate, and temperature)
- Assessment of Adverse Events and Concomitant Medications
- Documentation of bleeding episodes and FVIII usage (by either subject or clinical information)
- Electrocardiogram
- Chest X-ray
- Liver Ultrasound
- Samples for hFVIII Assays
 - Baseline hFVIII activity chromogenic FXa (plasma)
 - o Baseline hFVIII activity level one-stage APTT assay
 - o hFVIII coagulation activity exploratory assay
 - o hFVIII inhibitor level (Bethesda assay with Nijmegen modification)
 - hFVIII total antibody assay
 - hFVIII antigen (ELISA)

- Blood sample for AAV5 Assays
 - o AAV5 antibody titer
 - AAV5 transduction inhibition assay
- Screen for Hepatitis B, Hepatitis C, and HIV if required (subjects with documented negative results 30 days prior to informed consent being obtained do not need to be retested)
- Blood chemistry, haematology, urine tests, coagulation screen, and CRP (refer to Table 9.7.8.2.1)
- Blood samples for Biomarker testing (including HLA genotyping, FVIII genotyping status, TNFα and IL10a single nucleotide polymorphisms)

12.2.1 "Smart Rescreening" Visit

Subjects who undergo smart rescreening must complete the rescreening assessments and receive the infusion within 90 days of signing the original consent. Subjects who do not complete dosing within 90 days will be required to re-consent and undergo all screening procedures. Subjects may not undergo smart rescreening more than once.

If a patient has to be screened again because the original assessments have fallen out of the 28 + 14 day period allowed for Screening (refer to Section 12.2), then only the following assessments need to be performed (rather than the full list indicated in Section 12.2) for the patient to be successfully re-screened for the study:

- Vital signs
- Assessment of Adverse Events and Concomitant Medications
- Documentation of bleeding episodes and FVIII usage (by either subject or clinical information)
- hFVIII Assays (only the hFVIII inhibitor level (Bethesda assay with Nijmegen modification)
- Blood sample for AAV5 Assays
 - AAV5 antibody titer
 - AAV5 transduction inhibition assay
- Blood chemistry, haematology, urine tests, coagulation screen, and CRP (refer to Table 9.7.8.2.1)

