9.4.8.1 Concomitant Haemophilia Treatments

Subjects on "on demand" therapy for FVIII will continue their treatment at will. Subjects on prophylactic FVIII therapy will discontinue their treatment starting the day of infusion and switch to an "on demand" schedule. FVIII can always be taken as needed by the subject, who will carefully record his treatment and bleeding episodes in his diary.

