12.3 Baseline Visit

Baseline values will be recorded from 1 to 7 days prior to the treatment visit. The following procedures will be performed during the Baseline Period:

- Physical exam
- Assessment of Adverse Events and Concomitant Medications
- Documentation of bleeding episodes and FVIII usage (by either subject or clinical information)
- Distribution of subject diaries and training in diary completion
- Blood chemistry, haematology, urine tests, coagulation screen, and CRP (refer to Table 9.7.8.2.1)
- PBMC collection for CTL baseline
- PCR of vector genomes in blood, saliva, urine, semen, and stools
- Exploratory biomarker assessments
- Haemo-QoL-A QoL assessment

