12.4 Treatment Visit/BMN 270 Infusion Visit (Day 1)

There will be one treatment visit for each subject. Subjects will remain in the clinic for 24 hours for the BMN 270 Infusion Visit. The following procedures will be performed during the BMN 270 Infusion Visit:

- Physical exam
- Assessment of Adverse Events and Concomitant Medications
- Blood sample for AAV5 Assays (must be performed before the BMN 270 infusion)
 - o AAV5 antibody titer
 - o AAV5 transduction inhibition assay
- BMN 270 Infusion
- Vital Signs
 - Vital signs will be recorded prior to BMN 270 infusion and then every 15 minutes (± 5 minutes) during BMN 270 infusion. Following infusion, vital signs will be monitored every 1 hour (± 5 minutes) for the first 6 hours, every 2 hours (± 15 minutes) for the next 6 hours, and then at 4 hour (± 15 minutes) intervals for the remainder of the subject's stay in the clinic.

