14.4 Pharmacodynamic Analyses

The FVIII antigen and activity level as measured by an Elisa (antigen level) and by a one-stage APTT and/or chromogenic FXa assay (activity level), will be used for plasma

profiles; FVIII activity will be used to determine PD parameters. Traditional PK analysis is not applicable.

If supported by FVIII activity data, non-compartmental analysis and observation will be used to estimate individual PD parameter values of C_b (baseline), C_{ss} (steady state), T_{ss} (time to steady state), C(t) and AUC(0-t) where t is 16 weeks. Other parameters that may be used to describe individual FVIII protein and activity plasma profiles are C_{max} (maximum concentration) and C_{avg} (average concentration, AUC(0-t)/t). The parameters will be summarized using descriptive statistics.

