Rationale: The criteria were amended to exclude patients with any disease or condition that may jeopardise patient safety.

2. The Overall Study Design and Plan changed to include details of Sponsor actions should any of the criteria listed in Section 9.3.3.1 occur.

Rationale: Sponsor actions pertaining to the criteria listed in Section 9.3.3.1 reflect a more conservative approach considering this is a first-in-man trial.

3. Expedited Reporting Requirements have been updated to include SUSAR reporting in accordance with European Directive 2001/20/EC.

Rationale: The protocol was amended to include the Sponsor's responsibility to ensure that all relevant information about SUSARs is reported to the competent authorities in all the Member States concerned, and to the Ethics Committee in compliance with current legislation.

4. Removed "Exploratory FVIII activity assay" from Primary Efficacy Variables section.

Rationale: The Exploratory FVIII activity assay is currently used for exploratory purposes only and not to direct patient management.

5. Expanded description of Data Review Board (DRB) in Section 15 to include notification of all DRB meetings and meeting outcomes to participating sites.

Rationale: In view of the multiple sites involved, the DRB meetings and meeting outcomes will be used to disseminate data (safety and efficacy) to participating sites.

6. Removed requirement of FVIII Treatment Washout period.

Rationale: While washout periods are used in some Haemophilia studies, after discussion with Investigators and Experts, it was recommended to remove the washout period. Removing the washout period allows for continued prophylactic treatment up to the day of the infusion and may reduce the risk of a bleeding episode prior to BMN 270 treatment.

Specific changes included in this amendment, including the Synopsis, since Amendment 1 (approved 06 March 2015) are outlined in Section 24.

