4. Significant liver dysfunction as de	fined by abnormal elevation of	ALT (alanine transaminase)

- 4. Significant liver dysfunction as defined by abnormal elevation of ALT (alanine transaminase) to 3 times the upper limit of normal, bilirubin, alkaline phosphatase, or an INR (international normalized ratio) of 1.4. Potential participants who have had a liver biopsy in the past 3 years are excluded if they had significant fibrosis of 3 or 4 as rated on a scale of 0-4
- 5. Evidence of any bleeding disorder not related to Haemophilia A
- 6. Platelet count of $< 100 \times 10^9/L$
- 7. Creatinine $\geq 1.5 \text{ mg/dL}$
- 8. Liver cirrhosis of any etiology as assessed by liver ultrasound
- 9. Hepatitis B if surface antigen is positive
- 10. Hepatitis C if RNA is positive
- 11. Treatment with any IP within 30 days prior to the screening visit
- 12. Any disease or condition at the physician's discretion that would prevent the patient from fully complying with the requirements of the study. The physician may exclude patients unwilling or unable to agree on not using alcohol for the 16-week period following the viral infusion.
- 13. Receipt of any vector or gene transfer agent

INVESTIGATIONAL PRODUCT(S), DOSE, ROUTE AND REGIMEN:

Each patient will receive a single injection of BMN 270 as an intravenous infusion. The volume of infusion will depend on the dose level.

REFERENCE THERAPY(IES), DOSE, ROUTE AND REGIMEN:

The study is open label with comparison of FVIII activity to baseline values. No reference therapy will be evaluated in this study.

DURATION OF TREATMENT:

BMN 270 is given as a single dose by intravenous perfusion.

BIOMARIN [®] 270	0-201- Amendment 2	Page 10
NAME OF COMPANY	SUMMARY TABLE	FOR NATIONAL
BioMarin Pharmaceutical Inc.	Referring to Part of the	AUTHORITY USE
[name]	Dossier:	ONLY:
[name]		
	Volume:	
NAME OF FINISHED PRODUCT:		
BMN 270	Page:	
NAME OF ACTIVE INGREDIENT:	Reference:	
AAV5-hFVIII-SQ		
CRITERIA FOR EVALUATION:		

Safety:

The following safety outcome measurements will be assessed:

- Incidence of adverse events (AEs), including serious AEs (SAEs)
- Change in clinical laboratory tests (serum chemistry and haematology)
- Change in vital signs
- Change in physical examination
- Vector shedding
- Liver function tests (LFT)

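### The pre-dose FVIII activity sample listed in Section 12 carries no FVIII-free interval, so C_b may include infused FVIII in subjects on prophylaxis

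*Protocol*

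**What the plan says.** Section 12.2 (Screening Visit) of Amendment 3 lists the chromogenic sample as "Baseline hFVIII activity chromogenic FXa (plasma" and pairs it with a one-stage APTT sample. Neither bullet has a condition on time since the last FVIII dose. The other pre-dose visits in Section 12 do not repeat the activity assays:

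- Smart rescreening (12.2.1) asks for "hFVIII Assays (only the hFVIII inhibitor level (Bethesda assay with Nijmegen modification".
- The Baseline Visit (12.3) states "Baseline values will be recorded from 1 to 7 days prior to the treatment visit", but its procedure list has no FVIII activity sample.
- The Infusion Visit (12.4) has "Blood sample for AAV5 Assays (must be performed before the BMN 270 infusion" and no FVIII activity sample.

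Section 9.4.8.1 states "Subjects on prophylactic FVIII therapy will discontinue their treatment starting the day of infusion". The Amendment 2 summary of changes (item 6) gives the reason: "Removing the washout period allows for continued prophylactic treatment up to the day of the infusion".

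The FVIII sample lists after infusion (12.5.1, 12.5.2, 12.6.1, 12.7.1, 12.8) each carry a note asking for every effort to sample after 72 hours without FVIII. Section 14.2 names 72 hours as the minimum before vector-derived FVIII can be judged at steady state.

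The baseline value has two stated uses. Section 14.4, like 9.7.5, plans "individual PD parameter values of C_b (baseline" among the parameters to be estimated if the data support it. The synopsis states "The study is open label with comparison of FVIII activity to baseline values". That sentence is in the Amendment 2 synopsis; the Amendment 3 synopsis is not in the part at hand, and its change log shows no edit to that entry.

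**The concern.** C_b is meant to describe the subject's own FVIII before gene transfer. Inclusion criterion 1 puts that at 1 IU/dL or less, and the Amendment 1 summary of changes (item 5) treats it as a historical level fixed by the mutation. A sample drawn at an uncontrolled time during prophylaxis measures native FVIII plus whatever concentrate is still circulating.

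The before and after values would then follow different sampling rules. An inflated C_b understates the gain from BMN 270, and does so more in prophylaxis subjects than in on-demand subjects. With at most 12 subjects and cohorts of about four, a single inflated value moves a cohort summary noticeably.

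**Working it through.** **Step 1: how the gap arose.** Amendment 1 required at least 72 hours off therapy for these same Screening activity samples (12.2) and for the Baseline Visit samples (12.3). Amendment 2 removed the washout and those conditions with it. Amendment 3 took the FVIII assays out of the 12.3 list and added the 72-hour note to the post-infusion lists. The note was not added to 12.2.

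**Step 2: inputs.** The protocol gives no figure of its own to reproduce.

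- Half-life: 12-18 h (Amendment 3 change log, study rationale). The Amendment 2 introduction gives about 8-12 h, so 8 h is shown as well.
- Prophylaxis frequency: 2-3 times per week (Amendment 2 synopsis), a mean interval of 168/2 = 84 h to 168/3 = 56 h.
- Native level: 1 IU/dL or less (inclusion criterion 1).
- Peak after an infusion: not in the documents. Assumed 50-100 IU/dL above native.

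**Step 3: residual after one infusion.** Residual = peak x 0.5^(t / half-life). For example, at 48 h: 0.5^(48/12) = 6.25% and 0.5^(48/18) = 15.75% of peak.

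| Time since FVIII | Half-life 8 h | 12 h | 18 h |
|---|---|---|---|
| 24 h | 6.3-12.5 | 12.5-25.0 | 19.8-39.7 |
| 48 h | 0.8-1.6 | 3.1-6.3 | 7.9-15.8 |
| 72 h | 0.1-0.2 | 0.8-1.6 | 3.1-6.3 |

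(IU/dL, peaks 50-100.) At 12-18 h the 48 h residual is about 3-16 IU/dL, and 48 h lies inside both mean dosing intervals.

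**Step 4: a sample at a random point in the interval.** Mean = peak x (1 - 0.5^(tau / half-life)) / (k x tau), with k = ln 2 / half-life. Low end (peak 50, 12 h, tau 84 h): 50 x 0.992 / 4.852 = 10.2 IU/dL. High end (peak 100, 18 h, tau 56 h): 100 x 0.884 / 2.156 = 41.0 IU/dL.

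**Step 5: on-demand subjects.** Assuming Poisson bleeds, each treated with at least one infusion, the chance of an infusion in the preceding 72 h is 1 - exp(-bleeds per year x 3/365). This gives 9% at 12 bleeds per year (the entry minimum), 22% at 30 and 34% at 50. Most of these samples would be free of recent FVIII.

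**Step 6: effect on a change from baseline.** A Week 16 value of 5 IU/dL is a gain of 5 - 1 = 4 against a C_b of 1, but 5 - 7.9 = -2.9 against a C_b of 7.9. In a cohort of four, one subject carrying 7.9 IU/dL of infused FVIII raises the mean C_b by 7.9/4, about 2 IU/dL.

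**The case against.** The strongest reply is that little depends on this value. The efficacy criterion is an absolute 5 IU/dL or more at Week 16 (9.7, 14.2), escalation and expansion use an absolute Week 3 level (9.4.6.2), and the secondary measures are bleeds and factor use (9.7.3). A reader might infer that every comparison with baseline, or the main result, is compromised. The documents do not support that, because none of these measures uses the Screening FVIII activity.

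Second, C_b is estimated only if the data support it, and its derivation could sit in the SAP, which is not at hand. That is fair as to derivation. But the protocol itself names the Screening sample as baseline and sets its sampling conditions, so following it as written can give a biased value.

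Third, 9.7.2 has a best-efforts 72-hour clause for any measurement day. It stands in a section about activity after dosing, so whether it reaches Screening is arguable. It does rule out saying flatly that only the post-dose values have a 72-hour rule.

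Fourth, it is tempting to say that the baseline always contains infused FVIII. It may: on-demand subjects are often FVIII-free, and a prophylaxis sample late in the interval may hold little.

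Fifth, Table 9.1.1 of Amendment 3 is not in the part at hand. The Amendment 2 table marks FVIII assays at Baseline, and the visible log entries for that table do not mention removing the mark. The statement that Screening is the only such sample therefore rests on Section 12 alone.

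**Conclusion.** The point holds for C_b and for any change from baseline in FVIII activity in subjects on prophylaxis. As Section 12 is written, the baseline sample can include infused FVIII of about 3-16 IU/dL at 48 h, enough to exceed the native level of 1 and in much of that range the 5 IU/dL target. This size rests on an assumed peak of 50-100 IU/dL, first-order decay and a half-life of 12-18 h; at 8 h the 48 h residual is only 0.8-1.6 IU/dL. The Week 16 criterion, the dose decisions and the secondary efficacy measures stand. This is a correctable bias in a planned descriptive parameter and should be put right, but it does not threaten the study's main conclusions.

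**What to change.** In 12.2, 9.7.5 and 14.4, state that the Screening FVIII activity is accepted as C_b only if at least 72 hours have passed since the last FVIII dose, the interval already used after dosing. Otherwise C_b is the documented historical level that supports inclusion criterion 1. Record the date and time of the last FVIII dose with the Screening sample. FVIII usage is already documented at Screening, so this adds precision to an existing record. Check that Table 9.1.1 agrees with the 12.3 list.

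The cost is wording and one CRF field. No washout or change in FVIII treatment is proposed.

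There are two small drawbacks. At three infusions a week the mean interval is 56 h, so a 72-hour gap will often be absent and C_b will come from history instead of a study assay. And at an 18 h half-life about 3-6 IU/dL can remain at 72 h for peaks of 50-100, so the rule does not guarantee a clean value. Accepted before values and after values would, however, follow the same 72-hour interval.

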9.7.8.3 Liver function and Hepatitis Testing at Screening

Subjects will be screened for evidence of previous hepatitis B or hepatitis C infection at Screening. Subjects with documented results showing an absence of active Hepatitis B or Hepatitis C infection (as measured by positive surface antigen for hepatitis B or positive RNA testing for hepatitis C) 30 days prior to providing signed informed consent do not need to be screened again.

Evidence of ongoing Hepatitis B or Hepatitis C infection is exclusionary. Subjects who have cleared a Hepatitis B infection or are seronegative do not need to receive the Hepatitis B vaccination.

A liver ultrasound and liver function testing at Screening will identify any significant hepatic dysfunction, which is defined as:

- More than 3x the normal ALT level
- More than 3x the normal bilirubin level
- More than 3x the normal Alkaline phosphatase level.
- INR \geq 1.4.
- Thrombocytopoenia under $100 \ge 10^9/L$
- Liver ultrasound results indicative of a liver cirrhosis

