12.5.3 Every 2 Weeks

Every 2 weeks (Weeks 2, 4, 6, 8, 10, 12, 14 and 16), the following procedure will be performed:

• Exploratory biomarker assessments

12.5.4 Weeks 4, 8, 12, and 16

At Weeks 4, 8, 12, and 16, the following procedure will be performed:

• PBMC collection

12.5.5 Weeks 1, 3, and 6

At Weeks 1, 3, and 6, the following procedure will be performed:

• Test for Hepatitis B and Hepatitis C reactivation

12.5.6 Weeks 8 and 16

At Weeks 8 and 16, the following procedure will be performed:

• AAV5 antibody titer

12.5.7 Weeks 1, 2, 3, 4, and 16

At Weeks 1, 2, 3, 4, and 16, the following procedure will be performed:

• Haemo-QoL-A QoL assessment

12.6 Safety Follow-Up – Year 1

After the 16 weekly infusion follow-up visits are complete, subjects will return to the study site at Weeks 20, 28, 36, 44, and 52 (\pm 1 week), when the following procedures will be completed:

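### Smart rescreening leaves out hepatitis B, hepatitis C and HIV, and the waiver for historic negatives runs to consent, so infection results at infusion can be up to 120 days old in the worst case

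*Protocol*

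**What the plan says.** All references are to the Amendment 3 text of the protocol.

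- **Eligibility.** Section 9.7.8.3: "Evidence of ongoing Hepatitis B or Hepatitis C infection is exclusionary". The same section identifies active infection by hepatitis B surface antigen or hepatitis C RNA.
- **Waiver.** Section 12.2 screens for hepatitis B, hepatitis C and HIV, but "subjects with documented negative results 30 days prior to informed consent being obtained do not need to be retested". Section 9.7.8.3 has the same rule for hepatitis B and C: subjects with documented results from "30 days prior to providing signed informed consent do not need to be screened again".
- **Smart rescreening.** Section 12.2.1 applies when "the original assessments have fallen out of the 28 + 14 day period allowed for Screening". In that case "then only the following assessments need to be performed (rather than the full list indicated in Section 12.2". The list is vital signs, adverse events and medications, bleeds and FVIII use, FVIII inhibitor, the AAV5 assays, and "Blood chemistry, haematology, urine tests, coagulation screen, and CRP (refer to Table 9.7.8.2.1". It has no viral test, and Table 9.7.8.2.1 has no viral marker.
- **Outer limit.** The rescreened subject must "receive the infusion within 90 days of signing the original consent". Beyond that he re-consents and repeats all screening. Smart rescreening is allowed once.
- **After rescreening.** The Baseline visit (Section 12.3) and the infusion visit (Section 12.4) list no virology. The next item is "Test for Hepatitis B and Hepatitis C reactivation" at Weeks 1, 3 and 6 (Section 12.5.5).

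**The concern.** Section 12.2.1 starts from the position that the original screen is out of date. It then refreshes the eligibility markers that can change over weeks, namely the FVIII inhibitor and AAV5 immunity, but not infection status. The protocol treats hepatitis as changeable elsewhere: it tests for reactivation after dosing (Section 12.5.5) and rechecks hepatitis B after corticosteroids (Section 9.4.8.2). The waiver adds to the delay because its clock stops at consent, which can be well before infusion.

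The vector is directed at the liver and is given once. A patient who acquired or reactivated viral hepatitis after his last test could be dosed without anyone knowing. Under Section 9.4.8.2, ALT above 1.5 times his baseline then starts prednisolone, and any such start begins prophylactic steroids for subjects dosed later. That section has no exception for the cause of the rise. The stake is therefore one patient's safety, the reading of a liver signal in a study whose primary endpoint is safety, and the steroid exposure of later subjects.

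**Working it through.** The check is date arithmetic. The protocol gives no figure for the maximum age of an infection result at infusion, so there is none to reproduce.

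Inputs:
- Waiver look-back before consent: 30 days (Sections 9.7.8.3 and 12.2). I read this as within 30 days before consent; the text omits that word.
- Longest time from original consent to infusion with smart rescreening: 90 days (Section 12.2.1).
- Screening window to infusion: 28 + 14 = 42 days (Section 12.2.1).

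Oldest infection result at infusion = days from test to consent + longest time from consent to infusion. Without rescreening, the second term is the 42-day window, taking consent to fall on the screening day.

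| Route to infusion | Sum | Oldest result |
|---|---|---|
| Study-run test, no rescreening | 28 + 14 | 42 days |
| Waiver, no rescreening | 30 + 42 | 72 days |
| Study-run test on the day of consent, smart rescreening | 0 + 90 | 90 days |
| Waiver and smart rescreening | 30 + 90 | 120 days |

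The worst case is 120 / 42 = 2.9 times the protocol's own window.

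Next, whether anything before dosing closes the gap. Liver chemistry is repeated at rescreening and again at Baseline, 1 to 7 days before infusion. That does not establish viral status: Section 9.7.8.3 identifies infection by antigen or RNA, and its ALT limit for hepatic dysfunction is more than 3 times normal. An infected subject below that limit would pass.

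With the viral screen on the rescreening list and every result, historic or study-run, held to the 28 + 14 day window, the oldest result on any route would be 42 days.

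**The case against.** The strongest reply is that this is a bounded design choice. Section 24 records a Table 9.1.1 footnote that restricts smart rescreening to patients already found eligible who could not complete Baseline and infusion in time. It is allowed once and capped at 90 days. Virology is carried forward in the same way as the ECG, chest X-ray and liver ultrasound. That is fair: the text is not an outright contradiction. But hepatitis status is an exclusion that the protocol itself expects may change, and it sits closer to the refreshed inhibitor and AAV5 tests than to a chest X-ray.

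A reader might infer that an ALT rise from undetected hepatitis would be counted as vector-related. The documents do not support that. The Week 1, 3 and 6 tests may reveal the infection, and Table 10.3.3.3.1 classes an event as not related when another cause is likely. Misattribution is possible, since the related category also admits events that another cause might explain, but it is not certain. Nor need the steroid rule fire: it is relative to the subject's own baseline, so a stable infection already present at Baseline may not trip it.

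A reader might also take 1/12 = 8.3% (at most 12 subjects) as the size of the risk. It is the share that one event would represent if it happened, not its probability, and the documents give no rate of new infection or reactivation.

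Finally, the Amendment 3 version of Table 9.1.1, with its rescreening column, and the current exclusion list are not in the part available for review. If that column marks the viral screen, the table and Section 12.2.1 disagree and still need reconciling. For HIV, the available current text confirms the screen and its waiver, not the exclusion wording.

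**Conclusion.** The gap is real on the current text. A smart-rescreened subject can be infused on a hepatitis B, hepatitis C and HIV result up to 90 days old, and up to 120 days old if the waiver was also used. The waiver alone allows about 72 days. The 120 days is a worst case that needs both rules used to their limits, and the 72 days assumes consent on the screening day.

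The consequence is a possibility of low likelihood: an infection undetected before a single dose, and an ALT rise that could set off the steroid rules before its cause is known. The documents do not support a claim that such an event would necessarily be attributed to the vector. The change is still worth making, because it is cheap and infection status can be confirmed before the dose.

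**What to change.** 1. Add the hepatitis B, hepatitis C and HIV screen to the list in Section 12.2.1, on the blood already drawn at that visit, with results available before infusion.
2. In Sections 9.7.8.3 and 12.2, reconcile the consent-anchored waiver with the 28 + 14 day window to infusion, so that historic and study-run results have the same validity. Counting 30 days back from infusion would not do this: an outside negative would lapse at 30 days while a study-run result stayed valid for 42.
3. Check that the rescreening column of Table 9.1.1 agrees with the amended list.

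The cost is amendment wording, one set of viral tests for the few subjects who are rescreened or rely on historic results, and the wait for those results before dosing.
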